8.5.2. Data and Safety Monitoring Board

The DSMB, composed of external/independent subject matter experts, will conduct both, a scheduled unblinded review of safety data and as needed reviews of safety data if any pause rule is met or as otherwise requested by the study team and/or IST as described in the DSMB charter.

8.5.3. Cardiac Event Adjudication Committee

An independent Cardiac Event Adjudication Committee (CEAC) that includes pediatric and adult cardiologists will review suspected cases of myocarditis and pericarditis to determine if they meet CDC criteria of "probable" or "confirmed" events, and to assess severity (Gargano et al 2021). Any cases that the CEAC assesses as representing probable or confirmed cases of myocarditis or pericarditis will be referred to the Sponsor, who will then make a final decision on whether to suspend further enrollment and/or study dosing based on an assessment of the overall potential risk to study participants.

The CEAC will operate under the rules of an approved charter that will be written and reviewed at the organizational meeting of the CEAC. Details regarding the CEAC composition, responsibilities, procedures, and frequency of data review will be defined in its charter.

8.6. Treatment of Overdose

As the study treatment is to be administered by an HCP, it is unlikely that an overdose will occur. Dose deviations will be tracked as protocol deviations (Section 11.1.8).

mRNA-1073

8.7. Pharmacokinetics

Pharmacokinetic parameters are not evaluated in this study.

8.8. Pharmacodynamics

Pharmacodynamic parameters are not evaluated in this study.

8.9. Biomarkers

Immunogenicity assessments are described in Section 8.2. Samples for potential biomarker analysis will be collected from all participants. Transcriptomic and genomic samples will be part of the optional biomarker assessment once consented by the study participant. Exploratory assessments may include assessment of biomarkers for safety, reactogenicity, and inflammation. Serologic markers of disease severity, immune response to SARS-CoV-2 or influenza, RT-PCR of NP swab or saliva samples, genetic sequences of SARS-CoV-2 or influenza strains isolated from participants' samples, and genomic and transcriptomic samples may also be evaluated.

8.10. Health Economics

Health economics are not evaluated in this study.

9. STATISTICAL ANALYSIS PLAN

This section summarizes the planned statistical analysis strategy and procedures for the study. The details of statistical analysis will be provided in the statistical analysis plan (SAP), which will be finalized before the clinical database lock for the study. If changes are made to primary and/or secondary objectives or the related statistical methods after the study has begun, then the protocol will be amended (consistent with ICH Guideline E9). Changes to other secondary or exploratory analyses made after the protocol has been finalized, along with an explanation as to when and why they occurred, will be listed in the SAP or clinical study report (CSR) for the study. Ad hoc exploratory analyses, if any, will be clearly identified in the CSR.

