9.1. Blinding and Responsibility for Analyses

This is an observer-blind study. The investigator, study staff, study participants, site monitors, and Sponsor personnel (or its designees) will be blinded to the IP administered until the study database is locked and unblinded, with the following exceptions:

- Unblinded personnel (of limited number) will be assigned to vaccine accountability
 procedures and will prepare the IP for all participants. These personnel will have no study
 functions other than IP management, documentation, accountability, preparation, and
 administration. They will not be involved in participant evaluations and will not reveal
 the identity of the IP to either the participant or the blinded study site personnel involved
 in the conduct of the study unless this information is necessary in the case of an
 emergency.
- Unblinded medically qualified study site personnel will administer the IP. They will not be involved in assessments of any study endpoints.
- Unblinded site monitors, not involved in other aspects of monitoring, will be assigned as the IP accountability monitors. They will have responsibilities to ensure that sites are following all proper IP accountability, preparation, and administration procedures.
- An independent unblinded statistical and programming team will perform the preplanned IA (Section 9.6). Sponsor team members will be prespecified to be unblinded to the IA results and will not communicate the results to the blinded investigators, study site staff, clinical monitors, or participants.
- The DSMB will review unblinded safety data provided by the independent unblinded statistician to safeguard the interests of clinical study participants and to help ensure the integrity of the study. The DSMB will review unblinded statistical outputs for ad hoc safety reviews triggered by pause rules, should this occur. Section 11.1.11 provides additional information on DSMB and safety review.

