9.5.3. Immunogenicity Analysis

The analyses of immunogenicity will be based on the PP set. If the number of participants in the FAS and PP set differs (defined as the difference divided by the total number of participants in the PP set) by more than 10%, supportive analyses of immunogenicity may be conducted using the FAS.

For the immunogenicity endpoints, the geometric mean of specific antibody titers with corresponding 95% CI at each time point and the geometric mean fold rise (GMFR) of specific antibody titers with the corresponding 95% CI at each post-baseline time point over pre-injection baseline at Day 1 will be provided by treatment arm, with adjustment for baseline antibody titer and other potential covariates, including age group and primary vaccine type. Descriptive summary statistics, including median, minimum, and maximum, will also be provided.

For summarizations of geometric mean titer, antibody titers reported as below the lower limit of quantification (LLOQ) will be replaced by $0.5 \times LLOQ$. Values that are greater than the upper limit of quantification (ULOQ) will be converted to the ULOQ.

For mRNA-1010, seroconversion rate from baseline will be provided with a 2-sided 95% CI using the Clopper-Pearson method at each post-baseline time point. Rate of seroconversion is defined as the proportion of participants with either a pre-vaccination HAI titer < 1:10 and a post-vaccination HAI titer $\ge 1:40$ or a pre-vaccination HAI titer $\ge 1:10$ and a minimum 4-fold rise in post-vaccination HAI antibody titer.

For mRNA-1273, seroresponse is defined as either: participants with GMFR in nAb or bAb titers of \geq 4-fold at Day 29 compared to Day 1 in those with baseline titer \geq LLOQ, or Day 29 titer \geq 4 × LLOQ if baseline titer is < LLOQ.

The immunogenicity of mRNA-1073 will follow the same rules as mRNA-1010 and mRNA-1273.

Between-group comparisons will be evaluated in terms of immunogenicity endpoints (GMR and SCR/SRR difference) in the PP set and will be specified in the SAP in greater detail.

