9.5.4. Exploratory Analyses

Exploratory analyses not addressed in Section 9.5.3 will be described in the SAP before database lock.

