9.6.1. Interim Analysis

An IA will be performed after all the 550 participants randomized into Group 1 through Group 6 have completed their Day 29 visit assessments and will include the safety and immunogenicity data collected up to Day 29. Either nAb or bAb assay will be used for assessment of immunogenicity. The IA will be performed by a separate team of unblinded programmers and statisticians. The analysis will be presented by vaccination groups. Except for a limited number of Sponsor and CRO personnel who will be unblinded to perform the IA, the study site staff,

mRNA-1073

investigators, study monitors, and participants will remain blinded until after the final database lock for final analysis.

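### The protocol lets the SAP be finalized after the unblinded Day 29 interim analysis of all 550 participants, while some immunogenicity choices are still open

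*Protocol*

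**What the plan says.** Section 9 of the protocol sends the details of the analysis to a separate plan: they are to be "provided in the statistical analysis plan (SAP), which will be finalized before the clinical database lock for the study". Section 9.5.4 uses the same limit: "Exploratory analyses not addressed in Section 9.5.3 will be described in the SAP before database lock". Section 9.6 refers to the SAP for more on the interim and final analyses but gives no date.

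On the interim analysis, Section 9.6.1 says: "An IA will be performed after all the 550 participants randomized into Group 1 through Group 6 have completed their Day 29 visit assessments". It "will include the safety and immunogenicity data collected up to Day 29". On format and staffing it adds: "The analysis will be presented by vaccination groups" and "The IA will be performed by a separate team of unblinded programmers and statisticians". Section 9.1 states: "Sponsor team members will be prespecified to be unblinded to the IA results". Those members may not pass results to blinded investigators, site staff, clinical monitors or participants.

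Section 9.5.3 plans between-group comparisons (geometric mean ratio and difference in seroconversion or seroresponse rate) "in the PP set and will be specified in the SAP in greater detail". The only lock named in Section 9.6.1 is the final one, and Section 9.6.2 places the final analysis after every participant's Day 181 visit.

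**The concern.** Because it covers the whole sample, the interim analysis is in substance the Day 29 analysis of the trial. A SAP signed after it, but before the study lock, would comply with Section 9. It could not be called prespecified for the Day 29 immunogenicity endpoints.

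This matters because of how the data will be used. The main rationale for Amendment 2 says that data from these participants will support the choice of a dose level for Phase 2/3, and Section 4.2 gives enabling a Phase 2/3 study as the purpose of the trial. Readers will look at contrasts between the mRNA-1073 groups, the co-administration group and the single-vaccine groups. Choices of assay, covariates or per-protocol exclusions made with those contrasts in view can shift them, even where nothing is formally tested.

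**Working it through.** This is a check of sequence. The protocol attaches no power or error rate to it.

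1. **Coverage of the interim analysis.** Table 3 has one group of 50 and five of 100: 50 + 5 × 100 = 550, which reproduces the protocol's figure. Share of the sample in the interim analysis: 550/550 = 100%.

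2. **Order of events.** All Day 29 visits are completed; the unblinded analysis is presented by group; Sponsor members see it; Day 181 visits are completed; the final database lock and final analysis follow. The SAP deadline is tied to the lock. No interim lock is named. Section 9 speaks of the lock for the study, and Section 9.1 keeps the general blind until the study database is locked. Reading the deadline as an interim lock therefore has no support in the text.

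3. **Spacing of the visits.** For one participant, 181 − 29 = 152 days. With the Table 1 windows (−7/+2 at Day 29, ±14 at Day 181), the shortest gap is (181 − 14) − (29 + 2) = 136 days and the longest is (181 + 14) − (29 − 7) = 173 days. This is a visit-to-visit interval. Time for assays, cleaning and analysis before results, and for cleaning before lock, is not stated, so the interval from results to lock cannot be derived.

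4. **What is fixed and what is open.**

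| Item | In the protocol | Left open |
|---|---|---|
| Covariates (9.5.3) | Baseline titer, age group, primary vaccine type | Any others; the list is not closed |
| Group comparisons (9.5.3) | Measures and analysis set | Details |
| SARS-CoV-2 assay (8.2, 9.6.1, 9.6.2) | Neutralizing or binding antibody, by timing of data delivery | Which one, at each analysis |
| Per-protocol set (9.4, 6.5.3) | Main criteria; list of medications and vaccines | Which deviations exclude; listed medications only may exclude |
| Age-specific analyses (9.5.5) | May be done | Whether and how |
| Exploratory analyses (9.5.4) | To be in the SAP | Content |

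5. **Endpoints affected.** The open items bear on the Day 29 secondary immunogenicity endpoints. The solicited-reaction and unsolicited-event primary endpoints are counts, percentages and exact intervals on the safety sets (Sections 9.4 and 9.5.2). Covariates and per-protocol exclusions do not enter them.

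**The case against.** The strongest reply is that the deadline is an outer limit and allows any earlier date. Section 9.6 expects the SAP to describe the interim analysis. Section 9.5.3 already fixes the seroconversion and seroresponse definitions, the quantification-limit rules, the named covariates and exact intervals for seroconversion. Section 9.4 requires that excluding deviations be prespecified. Section 9 demands an amendment if primary or secondary methods change, and an explanation of when and why for changes to other analyses. A separate team runs the interim analysis, few people are unblinded, and Section 9.2 rules out formal hypotheses.

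Most of this stands and limits the point. Three gaps remain. The amendment rule governs changes to stated methods; it does not govern the first specification of open ones. Section 9.4 does not say by when deviations must be prespecified. The restriction on unblinded Sponsor members in Section 9.1 does not keep them from working on the SAP.

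A reader might infer more than the text supports:
- *That the SAP was finalized late, or about five months after results.* The SAP and its date are not shown, and the 152 days separate two visits.
- *That two of the three primary endpoints are compromised.* They are simple summaries that the open choices hardly touch.
- *That the interim analysis holds complete 28-day adverse event data.* The Day 29 visit may fall as early as 29 − 7 = Day 22, so some follow-up may be incomplete.
- *That the interim analysis is named as the basis for dose selection.* The protocol says this of the trial's data; that the interim results will drive it is a reasonable inference, not a statement.

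**Conclusion.** The concern holds as a statement of what the protocol permits. The SAP deadline falls after an unblinded, by-group analysis of 100% of participants through Day 29, and nothing requires the SAP to be final before it. The immunogenicity choices listed as open could therefore be settled with group results known.

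The size is modest. No type I error, margin or success criterion is at stake, and the core definitions and methods are already set. What is at risk is the credibility of descriptive immunogenicity contrasts in a trial meant to inform dose choice. The conclusion assumes that the lock in Sections 9 and 9.5.4 is the study lock, as the wording indicates, and that no other document sets an earlier SAP date.

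**What to change.** Change the deadline in Section 9 to: *The SAP will be finalized before any unblinding to group-level results for the interim analysis; later changes will be dated and identified as made after the IA.* Align Section 9.5.4 with it. Tying the deadline to unblinding for the interim analysis means that the safety reviews by the data and safety monitoring board do not trigger it.

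The cost is an earlier SAP sign-off. No sample size, visit or procedure changes.

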9.1. Blinding and Responsibility for Analyses

This is an observer-blind study. The investigator, study staff, study participants, site monitors, and Sponsor personnel (or its designees) will be blinded to the IP administered until the study database is locked and unblinded, with the following exceptions:

- Unblinded personnel (of limited number) will be assigned to vaccine accountability
 procedures and will prepare the IP for all participants. These personnel will have no study
 functions other than IP management, documentation, accountability, preparation, and
 administration. They will not be involved in participant evaluations and will not reveal
 the identity of the IP to either the participant or the blinded study site personnel involved
 in the conduct of the study unless this information is necessary in the case of an
 emergency.
- Unblinded medically qualified study site personnel will administer the IP. They will not be involved in assessments of any study endpoints.
- Unblinded site monitors, not involved in other aspects of monitoring, will be assigned as the IP accountability monitors. They will have responsibilities to ensure that sites are following all proper IP accountability, preparation, and administration procedures.
- An independent unblinded statistical and programming team will perform the preplanned IA (Section 9.6). Sponsor team members will be prespecified to be unblinded to the IA results and will not communicate the results to the blinded investigators, study site staff, clinical monitors, or participants.
- The DSMB will review unblinded safety data provided by the independent unblinded statistician to safeguard the interests of clinical study participants and to help ensure the integrity of the study. The DSMB will review unblinded statistical outputs for ad hoc safety reviews triggered by pause rules, should this occur. Section 11.1.11 provides additional information on DSMB and safety review.

The treatment assignment, including the injection site and the corresponding vaccine or placebo administered, will be concealed by having the unblinded pharmacy personnel prepare the IP in a secure location that is not accessible or visible to other study staff. An opaque sleeve over the syringe used for injection will maintain the blind at the time of injection, as the doses containing mRNA will look different from those of placebo. Only delegated unblinded study site staff will conduct the injection procedure. Once the injection is completed, only the blinded study staff will perform further assessments and interact with the participants. Access to the randomization code will be strictly controlled at the pharmacy.

9.1.1. Breaking the Blind

Except in the case of medical necessity, a participant's vaccine assignment should not be unblinded without the approval of the Sponsor. If a participant becomes seriously ill or pregnant during the study, the blind will be broken only if knowledge of the vaccine assignment will affect that participant's clinical management. In the event of a medical emergency requiring identification of individual vaccine assignment, the investigator will make every attempt to contact the CRO's medical monitor, preferably via electronic protocol inquiry platform, to explain the need for unblinding within 24 hours of opening the code. The investigator will be responsible for documenting the time, date, reason for unblinding, and the names of the personnel involved. The investigator (or designee) will have access to unblind participants within interactive response technology (IRT). All unblinding instances will be tracked via an audit trail in IRT and documented in the final study report.

If unblinding should occur (by either accidental unblinding or emergency unblinding) before completion of the study, the investigator must promptly contact the Sponsor and document the circumstances on the appropriate forms.

In addition to the aforementioned situations where the blind may be broken, the data will also be unblinded to a statistical team at specified time point(s) for analysis as outlined in Section 9.1.

9.2. Statistical Hypotheses

No formal hypotheses will be tested. All analyses will be descriptive and presented by vaccine group.

9.3. Sample Size Determination

The sample size for this study is not driven by statistical assumptions for formal hypothesis testing. The number of proposed participants is considered sufficient to provide a descriptive summary of the safety and immunogenicity of different study groups.

The study will enroll approximately 550 generally healthy adults 18 to 75 years of age who were previously fully vaccinated for COVID-19 primary series with a locally authorized and approved SARS-CoV-2 vaccine, and their last COVID-19 vaccine must be \geq 120 days prior to the randomization visit (or less per local guidance). Participants must not have received a licensed influenza vaccine within \leq 180 days of randomization and have not had known history of confirmed influenza infection within \leq 180 days or SARS-CoV-2 infection within \leq 90 days of Screening. The number of participants and groups are shown in Table 3.

Approximately 550 participants will be enrolled at a CCI Asample size of 100 participants in one group has at least an 85% (or 95%) probability to observe at least 1 participant with an AE at a true 2% (or 3%) AE rate (Table 7).

Table 7 Randomized Sample Size Calculations

Sample Size	True AE Rate	Probability to Observe 0 AEs	Power to Detect at Least 1 AE
50	0.05	7.7%	92.3%
50	0.03	21.8%	78.2%
100	0.03	4.8%	95.2%
100	0.02	13.3%	86.7%

Abbreviation: AE = adverse event.

9.4. Analysis Sets

The analysis sets are described in Table 8.

Table 8 Analysis Sets

Set	Description	
Randomization Set	The randomization set consists of all participants who are randomly assigned.	
FAS ¹	The FAS consists of all randomly assigned participants who receive the IP.	
PP Set ²	The PP set consists of all participants in the FAS who comply with the injection schedule, comply with the timings of immunogenicity blood sampling to have a baseline and at least 1 post-injection assessment, do not have influenza or SARS-CoV-2 infection at baseline and post-baseline up to Day 29 (as documented by positive RT-PCR testing result), and have no major protocol deviations and/or prohibited concomitant medication use (documented in the Section 6.5.3) that are prespecified with impacts on the immune response and should be excluded from the PP set.	
Safety Set ³	The safety set consists of all randomly assigned participants who receive the IP.	

Set	Description	
Solicited Safety Set ⁴	The solicited safety set consists of all participants in the safety set who contribute any solicited AR data.	

Abbreviations: AR = adverse reaction; FAS = full analysis set; IP = investigational product; PP = per-protocol.

- ¹ For the FAS, participants will be analyzed according to the group to which they were randomized.
- ² The PP set will be used as the primary analysis set for analyses of immunogenicity unless otherwise specified. Participants will be analyzed according to the group to which they were randomized.
- ³ The safety set will be used for all analyses of safety, except for the solicited ARs. Participants will be included in the vaccination group corresponding to what they actually received.
- ⁴ The solicited safety set will be used for the analyses of solicited ARs and participants will be included in the vaccination group corresponding to what they actually received.

